Study Protocol

Total Hip Replacement (THR) is a common surgical procedure performed in patients who do not respond to long-term conservative treatment to reduce high pain sensation and movement limitation in the joint (Li and Xu, 2018). Physiotherapy and rehabilitation routinely applied to regain functional independence in daily living, restore pain and joint range of motion, eliminate muscle weakness, regulate walking pattern, prevent falls, loosening, revision surgery and dislocations in the prosthesis, increase participation in activities of daily living (ADL), quality of life (QoL) and patient satisfaction levels after THR (Louw et al., 2013; Galea et al., 2008). It was determined in Kennedy et al. (2017) that patients have education expectations on recognition of the surgical team, general information about the disease and prosthesis, rehabilitation, pain management, home care activities, complications, medications, ADL after THR surgery. At the present time, with the help of demographic changes in the society and patients, changes in healthcare provision, and technological approaches, discharge education became more effective with video assistance (Abu Abed et al., 2014). The aim of our study was to investigate the effect of a video-assisted discharge education program on activities of daily living, functionality, and patient satisfaction after total hip replacement surgery.

Methods:

The study was approved by the Non-invasive Clinical Researches Ethics Committee (60116787-020/58408) on 04.09.2018. The participants included in the study were informed about the study and informed consent form was signed by all participants. Our study was performed between September 2018 and June 2019.

Of the 36 participants who met the inclusion criteria, 5 were excluded from the study for missing follow-ups or not wanting to participate in the study. The 31 participants included

in the study were randomized using systematic sampling. According to last number of file numbers odd numbers included in the physiotherapy (PT) group (n=18), and even numbers included in the video-assisted discharge education (VADE) group (n=13). The first meeting with participants was made in the hospital room within the first 5 days after THR surgery in both groups. Participants and their relatives were given physiotherapy and video-assisted discharge education by the same physiotherapist without being told which group they were in.

The physiotherapy program given to the PT group included breathing exercises, positioning, hip range of motion and strengthening exercises, and information about walking and ambulation. The whole program was taught verbally and practically to participants and their relatives. Information was given about the exercises to be added at the end of the first week and in the 4th week. A physiotherapy booklet prepared with the same content was given to the participants. The booklet was examined by the patient and relatives, and the questions they asked were answered by the same physiotherapist. The participants were informed that they should continue the exercises for 12 weeks.

VADE group received video-assisted discharge education in addition to the physiotherapy program given to the PT group on the same day by the same physiotherapist. The VADE program included information about THR, preventive rehabilitation approaches, transfer activities, using stairs, self-care activities, home settings by modifying the treatment and discharge protocols of Lucas (2008). VADE was prepared as a presentation of written information and videos which is shown this information by a professional model. Video shoots were done by a physiotherapist experienced in the field of physiotherapy and rehabilitation after THR surgery. The presentation was stopped when participants have questions or have points were not understood and the necessary explanations were shown verbally and practically. Along with the physiotherapy booklet, the participants were given an educational booklet containing written and visual information prepared in the same content as VADE. The booklet was

examined by the patient and relatives during VADE, and the questions they asked were answered by the same physiotherapist.

Patient interviews were completed in approximately 30 minutes in the PT group and approximately 45 minutes in the VADE group. A healthy person was used to prevent damage to the hip joints of those who had undergone surgery in photographs and videos in the VADE and booklets. In the booklets, easily understandable sentences were used by participants and their relatives. Booklets were prepared in Arial font and 11-point size. All participants were called by phone every 15 days for 12 weeks, and their participation in the exercises and ADL was followed.

Assessments were performed within the first 5 days after the THR surgery (Descriptive Information, Pain, Patient Satisfaction Questionnaire) in the hospital room after physiotherapy and VADE programs, and at the 3rd-month control (Pain, Harris Hip Score (HHS), Tampa Scale of Kinesiophobia (TSK), Nottingham Extended Activities of Daily Living Scale (NEADL), Patient Satisfaction Questionnaire) in orthopedics and traumatology clinic.

Statistical Analysis Plan

In the statistical analysis of data obtained in this study, Windows-based SPSS (IBM SPSS Statistics, Version 24.0, Armonk, NY, USA) package program was used. It was calculated that the number of patients included in our study was 89% power and 95% confidence for each group. Continuous variables were expressed as a mean \pm standard deviation or as a median (minimum-maximum values), and categorical variables as a number and percent. Analytical (Kolmogorov-Smirnov/Shapiro-Wilks test) and visual (Histogram and probability graphs) methods were used to test the conformity of data for normal distribution. When the parametric test assumptions were provided, Independent Sample T-Test was used to compare independent group differences; when the parametric test assumptions were not provided, Mann

Whitney-U test was used to compare independent group differences. In the dependent group analyzes; when the parametric test assumptions were provided, Paired Sample T-Test was used; when the parametric test assumptions were not provided, Wilcoxon Test was used. Chi-Square Analysis and Fisher Exact Test were used compare differences between categorical variables. The statistical significance level was assumed at $p < 0.05$ in this study.

Results

A total of 31 patients, aged between 25 and 70 years (PT Group= 55.33 ± 11.83 years, VADE Group= 49.61 ± 9.52 years) were included in this study. There was no significant difference in age, body mass index, daily work and standing times between the two groups ($p > 0.05$). Other demographic characteristics of the patients are presented in Table 1.

When the patients' pain perception levels were compared within the group, a statistically significant decrease in sleep, rest, and activity were detected between the 1st week and 3rd-month evaluations in both groups ($p < 0.05$). There was a statistically significant difference between groups in scores on resting pain levels in the 1st week and on resting and activity pain levels in the 3rd month in favor of the VADE group ($p < 0.05$) (Table 2).

While no difference was found between the groups in the pain levels sub-parameter of HHS ($p > 0.05$), there was a statistically significant difference in favor of the VADE group in function, absence of deformity and ROM scores and total scores ($p < 0.05$). When GYA levels were examined, no significant difference was found in the sub-parameters of NEADL in favor of the VADE group ($p > 0.05$), except for the movement score ($p < 0.05$). According to the results of TSK, the level of kinesiophobia of the VADE group was found to be statistically significantly lower than the PT group ($p < 0.05$) (Table 3). When patient satisfaction levels were compared, there was a statistically significant difference between groups on scores of all parameters in the

1st week and 3rd month significantly higher scores were seen in the VADE group versus to PT group ($p < 0.05$) (Table 4).

Table 1. Demographic Data of Patients

Variables	PT Group (n=18)		VADE Group (n=13)		p
	$\bar{x}\pm SD$		$\bar{x}\pm SD$		
Age (years)	55.33±11.83		49.61±9.52		0.16 ^a
BMI (kg/m ²)	26.86±2.68		26.07±2.50		0.41 ^a
Daily Working Times	2.00±3.67		5.15±5.28		0.11 ^b
Variables	PT Group		VADE Group		p
	n	%	n	%	
Sex					
Female	12	66.7	9	69.2	1.00 ^d
Male	6	33.3	4	30.8	
Use of Cement					
Cemented	6	33.3	3	23.1	0.69 ^d
Cementless	12	66.7	10	76.9	
Dominance on Upper Extremity					
Right	16	88.9	12	92.3	1.00 ^d
Left	2	11.1	1	7.7	
Dominance on Lower Extremity					
Right	12	66.7	10	76.9	0.69 ^d
Left	6	33.3	3	23.1	
Affected Extremity					
Right	8	44.4	7	53.8	0.60 ^c
Left	10	55.6	6	46.2	
Education level					
Illiterate	3	16.7	1	7.7	-
Primary school	7	38.9	4	30.8	-
Middle School	2	11.1	1	7.7	-
High school	4	22.2	4	30.8	-
Associate degree	1	5.6	1	7.7	-
Undergraduate degree	1	5.6	2	15.4	-
Profession					
Retired	5	27.7	3	23.07	-
Housewife	7	38.8	3	23.07	-
Worker	2	11.1	2	15.3	-
Officer	1	5.5	1	7.6	-
Teacher	1	5.5	1	7.6	-
Farmer	2	11.1	-	-	-
Artisan	-	-	1	7.6	-
Cleaning staff	-	-	1	7.6	-
Chef	-	-	1	7.6	-

PT: Physiotherapy, VADE: Video-assisted discharge education, BMI: Body Mass Index, kg: kilogram, m: meter, p<0.05: statistically significant difference, n: Sample size, \bar{x} : mean, SD: standard deviation, p^a: Independent Sample T-Test, p^b: Mann Whitney-U test, p^c: Chi-Square Analysis, p^d: Fisher Exact Test

Table 2. Comparison of Pain Levels of Patients

VAS (In-group)		PT Group		p
		1st week	3rd month	
		$\bar{x}\pm SD$	$\bar{x}\pm SD$	
Sleep		5.54±2.69	3.06±2.28	0.008 ^{a*}
Rest		6.97±1.72	3.86±2.05	0.000 ^{c*}
Activity		8.54±1.51	5.98±2.24	0.000 ^{a*}
VAS (In-group)		VADE Group		p
		1st week	3rd month	
		$\bar{x}\pm SD$	$\bar{x}\pm SD$	
Sleep		5.5±2.01	2.09±2.26	0.000 ^{a*}
Rest		4.8±2.67	2.02±1.51	0.005 ^{a*}
Activity		7.13±2.42	3.78±2.38	0.002 ^{a*}
VAS (Between groups)		PT Group	VADE Group	p
		Median (min-max)	Median (min-max)	
Sleep	1st week	4.9 (0-10)	5.4 (2.7-9.5)	0.96 ^a
	3rd month	2.5 (0-8.8)	1.5 (0-7.4)	0.13 ^b
Rest	1st week	6.8 (4.2-10)	5 (0-8.9)	0.01 ^{a*}
	3rd month	3.45 (4-8.40)	1.8 (0-4.5)	0.01 ^{a*}
Activity	1st week	8.9 (4.6-10)	7.4 (3-10)	0.13 ^b
	3rd month	5.5 (2.2-10)	3.5 (0-7.5)	0.01 ^{a*}

PT: Physiotherapy, VAS: Visual Analog Scale, VADE: Video-assisted discharge education, min: Minimum, max: Maximum, p<0.05: statistically significant difference, \bar{x} : mean, SD: standard deviation, p^a: Paired Sample T-Test, p^b: Mann Whitney-U test p^c: Wilcoxon Test

Table 3. Comparison of Hip Function, Activities of Daily Living and Kinesiophobia

HHS	PT Group		VADE Group		p
	$\bar{x}\pm SD$	Median (min- max)	$\bar{x}\pm SD$	Median (min- max)	
Pain	28.44±13.38	30 (10-44)	35.84±8.84	40 (20-44)	0.135 ^b
Function	29.22±10.22	29.5 (11-47)	40.07±5.80	39 (29-47)	0.002 ^{a*}
Absence of Deformity	1.50±1.20	1 (0-4)	3.15±0.80	3 (2-4)	0.000 ^{b*}
ROM	4.57±0.62	4.8 (2.5-5)	4.92±0.10	4.95 (4.69-5)	0.034 ^{b*}
Total	63.74±23.49	62.72 (23.5-98)	83.99±12.46	81.8 (66.85-100)	0.004 ^{b*}
NEADL	PT Group		VADE Group		p
	Median (min-max)		Median (min-max)		
Movement	13 (5-18)		16 (7-18)		0.038 ^{b*}
Kitchen Activities	12 (3-15)		15 (7-15)		0.106 ^b
Housework	11 (2-15)		13 (9-15)		0.146 ^b
Leisure-time Activities	12 (5-18)		15 (4-18)		0.352 ^b
Total	47.5 (17-66)		59 (41.64)		0.170 ^b
TSK	PT Group		VADE Group		p
	$\bar{x}\pm SD$		$\bar{x}\pm SD$		
Total	48.05±6.59		39.38±8.13		0.003 ^{a*}

PT: Physiotherapy, VADE: Video-assisted discharge education, ROM: Range of motion, HHS: Harris Hip Score, NEADL: Nottingham Extended Activities of Daily Living Scale, TSK: Tampa Scale of Kinesiophobia, min: Minimum, max: Maximum, p<0.05: statistically significant difference, \bar{x} : mean, SD: standard deviation, p^a: Independent Sample T-Test, p^b: Mann Whitney-U test.

Table 4. Comparison of Patient Satisfaction Levels

Patient Satisfaction Questionnaire (In-group)		PT Group		p
		1st week	3rd month	
		$\bar{x}\pm SD$	$\bar{x}\pm SD$	
Surgical Procedure		5.15±2.56	5.77±2.29	0.123 ^a
Physiotherapy or VADE Program		6.38±2.93	6.87±2.46	0.273 ^a
ADL and Prevention Protocols		6.06±2.66	7.01±2.34	0.028 ^{a*}
Transfer Activities		6.67±2.20	6.85±2.24	0.705 ^a
Home Settings		6.17±2.16	6.62±2.12	0.201 ^a
Patient Satisfaction Questionnaire (In-group)		VADE Group		p
		1st week	3rd month	
		$\bar{x}\pm SD$	$\bar{x}\pm SD$	
Surgical Procedure		8.35±1.51	8.62±1.12	0.615 ^a
Physiotherapy or VADE Program		9.12±0.89	9.46±0.64	0.279 ^a
ADL and Prevention Protocols		8.96±1.34	9.48±0.52	0.251 ^a
Transfer Activities		9.13±1.06	9.72±0.36	0.091 ^c
Home Settings		8.57±1.95	9.52±0.55	0.068 ^c
Patient Satisfaction Questionnaire (Between groups)		PT Group	VADE Group	p
		Median (min-max)		
		Median (min-max)		
Surgical Procedure	1st week	5.6 (0.4-8.9)	8.5 (4.7-10)	0.000 ^{a*}
	3rd month	5.7 (1.2-8.5)	8.6 (6.8-10)	0.000 ^{a*}
Physiotherapy or VADE Program	1st week	7.2 (0-10)	9.3 (7.2-10)	0.001 ^{a*}
	3rd month	7.2 (2.3-10)	9.6 (8.2-10)	0.001 ^{b*}
ADL and Prevention Protocols	1st week	6.2 (0-10)	9.6 (6-10)	0.000 ^{b*}
	3rd month	7.3 (2.8-10)	9.5 (8.5-10)	0.001 ^{b*}
Transfer Activities	1st week	6.5 (3.3-10)	9.5 (6.3-10)	0.001 ^{b*}
	3rd month	6.95 (2.4-10)	10 (9-10)	0.000 ^{b*}
Home Settings	1st week	63.5 (26-96)	92 (31-100)	0.001 ^{b*}
	3rd month	71 (30-96)	97 (83-100)	0.000 ^{b*}

PT: Physiotherapy, VADE: Video-assisted discharge education, min: Minimum, max: Maximum, ADL: Activities of daily living, p<0.05: statistically significant difference, \bar{x} : mean, SD: standard deviation, p^a: Paired Sample T-Test, p^b: Mann Whitney-U test p^c: Wilcoxon Test

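### Five of 36 eligible patients were removed partly for missed follow-up, yet allocation is described only for the remaining 31, so the month-3 comparisons may be completers-only.

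*Combined protocol and SAP*

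**What the plan says.** The participant paragraph of the Methods starts from 36 eligible patients, of whom "5 were excluded from the study for missing follow-ups or not wanting to participate in the study". The 31 who remained "in the study were randomized using systematic sampling". The rule was the last digit of the file number: "According to last number of file numbers odd numbers included in the physiotherapy (PT) group (n=18"), with even digits going to VADE (n=13).

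The later Methods paragraphs describe two kinds of follow-up. One is telephone contact: "All participants were called by phone every 15 days for 12 weeks". The other is the final assessment. Measurements were taken "in the hospital room after physiotherapy and VADE programs, and at the 3rd-month control", so even the week-1 pain and satisfaction scores came after the arm-specific teaching.

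The Statistical Analysis Plan defines no analysis set and no handling of missing data. The Results open with "A total of 31 patients, aged between 25 and 70 years". Table 1 gives 18 and 13 as the group sizes; Tables 2 to 4 print no numbers of patients.

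**The concern.** One pooled count covers two events with different consequences. A refusal before allocation narrows the population to which the results apply, but does not bias the comparison of arms. A loss after the arm-specific session can bias it. The text gives no split by reason, timing or arm, so a reader cannot tell how many of the five belong to each kind.

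The order given (exclude, then randomize) does not fit missed follow-up as a reason, because no follow-up is described before the session at which the arms diverge. If some of the five were lost after that session, the month-3 results compare completers only. Any week-1 pain and satisfaction data from those patients may also have been left out; the document does not say.

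The aim is to "investigate the effect of a video-assisted discharge education program on activities of daily living, functionality, and patient satisfaction". In the activities-of-daily-living results, NEADL showed no significant difference "except for the movement score", so the one positive finding in that domain rests on p=0.038 with 31 patients.

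**Working it through.** **1. Counts.** 36 − 5 = 31 and 18 + 13 = 31, so the stated figures close and none of the five is in the reported groups. 5/36 = 13.9% is an upper bound on loss after allocation. As a partial check on Table 3, equal-variance t-tests with n = 18 and 13 give p = 0.0027 for TSK (reported 0.003) and 0.0018 for HHS function (reported 0.002). Those rows are consistent with all 31; the other rows were not verified in this way.

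**2. Sequence.** The hospital session took place within 5 days of surgery and delivered the arm-specific programme. The calls ran over the next 12 weeks and the control was at month 3. A missed follow-up in the sense the document uses therefore falls after the session. Arm was fixed by file-number parity, so it was knowable for all five.

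**3. Possible extent.** Losses after allocation number 1 to 4 if both named reasons occurred, and 0 to 5 otherwise. With five losses, the extremes are 5/(13+5) = 27.8% of VADE and none of PT, or 5/(18+5) = 21.7% of PT and none of VADE. A 3 PT/2 VADE split gives 3/21 = 14.3% and 2/15 = 13.3%.

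**4. NEADL movement (Table 3: PT median 13, VADE median 16, Mann-Whitney p=0.038).** With a normal approximation and ties ignored, mean U = n₁n₂/2 and SD = √[n₁n₂(n₁+n₂+1)/12]. For 13 and 18 these are 117 and 24.98. p=0.038 gives z = 2.075, so U = 117 + 2.075 × 24.98 = 168.8. A VADE loss at the PT median outranks half of the 18 PT patients and adds 9 to U. A PT loss at the VADE median adds 13/2 = 6.5.

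| Assumed losses | U | Mean | SD | z | p |
|---|---|---|---|---|---|
| 1 VADE at PT median | 177.8 | 126 | 26.32 | 1.97 | 0.049 |
| 2 VADE at PT median | 186.8 | 135 | 27.66 | 1.87 | 0.061 |
| 1 VADE below every PT patient | 168.8 | 126 | 26.32 | 1.63 | 0.10 |
| 1 PT at VADE median | 175.3 | 123.5 | 26.06 | 1.99 | 0.047 |
| 2 PT at VADE median | 181.8 | 130 | 27.14 | 1.91 | 0.056 |

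Rounding of 0.038 alone moves the first row between 0.048 and 0.050.

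**5. HHS total by ranks (Mann-Whitney p=0.004).** z = 2.878, so U = 117 + 2.878 × 24.98 = 188.9. One to four VADE losses at the PT median give p = 0.006, 0.009, 0.013 and 0.018. One to four VADE losses ranked below every PT patient give p = 0.017, 0.051, 0.12 and 0.24. Rounding of 0.004 (0.0035 to 0.0045) moves the 0.051 between 0.047 and 0.056.

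**6. HHS total from means and SDs.** Inputs are PT 63.74 ± 23.49 and VADE 83.99 ± 12.46: difference 20.25, Welch p=0.0045, equal-variance p=0.0085. Adding k patients at value x to an arm gives N = n+k, M = (nm+kx)/N and SD² = [(n−1)s² + n(m−M)² + k(x−M)²]/(N−1). Each lost patient is placed at the observed extreme of their own arm that narrows the difference: VADE 66.85, PT 98.

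- Four losses, any split: difference 14.0 to 16.2 and Welch p at most 0.035. The equal-variance p is 0.070 for 0 VADE/4 PT and 0.060 for 1/3.
- Five losses, 1 VADE/4 PT: VADE 82.77 ± 12.82 (n=14), PT 69.97 ± 25.09 (n=22), difference 12.80, Welch p=0.052, equal-variance p=0.087.
- Five losses, 0 VADE/5 PT: PT 71.19 ± 25.20 (n=23), difference 12.80, Welch p=0.050, equal-variance p=0.10.

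At the opposite extremes (VADE 100, PT 23.5), five PT losses widen the difference to 29.0. If the lost patients resemble the completers in their arm, the differences do not change.

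**The case against.** Read literally, the paragraph puts all five exclusions before allocation, and unwillingness to take part fits refusal at entry. The case for later loss rests on the two words about follow-up, and zero losses remains possible. This stands: loss after allocation is an inference, and the certain defect is that the text contradicts itself.

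The scenarios are assumed. One VADE loss at the PT median leaves NEADL movement marginally below 0.05, and the difference between 0.049 and 0.050 is finer than a U reconstructed from a rounded p can resolve. Any p near 0.04 would be similarly fragile. Movement is also one of five NEADL rows, the total already has p=0.170, and no primary outcome is named. All of this stands, so the figures show sensitivity and not harm.

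A reader might infer that VADE lost more patients because it ended with 13 against 18. The document does not support that: against a 50:50 expectation the exact two-sided binomial p is 0.47. Nor does it support reading all five as dropouts, or assuming that the bias favours VADE.

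The opposite temptation is to call the HHS result robust because four losses at own-arm extremes keep Welch p at or below 0.035. That depends on stopping at four and on choosing Welch, whereas Table 3 used Mann-Whitney. Section 5 and the five-loss cases above show that it can fail.

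**Conclusion.** The concern holds in a limited form. It is certain that the order of exclusion and allocation conflicts with a stated reason for exclusion, and that reason, timing and arm are not reported for 5 of 36 patients. It is probable, not shown, that anyone removed for missed follow-up had already been allocated and treated. The month-3 comparisons may therefore be completers-only, with 0 to 5 losses and bias of unknown size and direction.

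If losses occurred, one or two are enough to put NEADL movement at or beyond 0.05. HHS total tolerates VADE losses at the PT median, but not every plausible pattern. These statements rest on assumed outcomes, summary data and approximate tests, and the two endpoints serve as illustrations.

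**What to change.** - Rewrite the participant paragraph so that the order of exclusion and allocation agrees with the reasons given.
- Report the five by reason, timing and arm, with arm taken from file-number parity.
- Define the analysis set as all consenting patients in the arm fixed by their file number, with nobody excluded for missed follow-up. A set limited to those who received a first session could omit patients whose arm was already fixed.
- Include patients lost later in the week-1 pain and satisfaction comparisons where data exist and consent permits.
- If losses after allocation are confirmed, label the month-3 results as completers-only and add one sensitivity analysis that varies the assumed outcomes of lost patients in both arms and in both directions.
- If timing or arm cannot be recovered, state this as a limitation.

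The cost is a check of at most five files, a corrected paragraph and, only if losses are confirmed, one further analysis. The downside is that month-3 effects, NEADL movement especially, may look less certain.

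### Allocation by odd or even file number is labelled randomised, but the rule is deterministic and no concealment is described

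*Combined protocol and SAP*

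**What the plan says.** The Methods section of the combined protocol and SAP states that the 31 participants "in the study were randomized using systematic sampling". The next sentence sets out the assignment: "According to last number of file numbers odd numbers included in the physiotherapy (PT) group (n=18), and even numbers included" in the other arm, given in full as "even numbers included in the video-assisted discharge education (VADE) group (n=13"). No random sequence, generator, sealed envelope, central service or independent allocator is mentioned.

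The only statement about who did not know the assignment concerns participants and relatives, who received the programmes "by the same physiotherapist without being told which group they were in".

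Just before the allocation sentence, the Methods report that of 36 people meeting the inclusion criteria, "5 were excluded from the study for missing follow-ups or not wanting to participate in the study". Neither their arm nor the date of each exclusion is given.

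On baseline, the Results say: "There was no significant difference in age, body mass index, daily work and standing times between the two groups". On outcomes, they report, for example for the Harris Hip Score, that "there was a statistically significant difference in favor of the VADE group in function" and in other components, with no qualification about how the arms were formed.

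**The concern.** Randomisation makes two things true: the assignment is produced by chance, and, if it is concealed, nobody can act on it before the patient is in the study. A parity rule on an existing record number gives neither by construction. The arm is fixed before the patient is approached and can be read from the file. Systematic sampling, the term used, is a way of drawing a sample from a list, not of assigning treatment.

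Not telling participants their group is blinding. It does not stop the person who screens or invites from knowing which programme a patient would receive. The same physiotherapist delivered both programmes, and the documents do not say who recruited or who could see file numbers first.

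At stake is how the differences in favour of VADE may be read. If invitation, refusal or loss depended on the foreseeable arm, part of a difference could reflect who ended up in each arm. A reader or evidence synthesiser who relies on the label would assume this route was closed.

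The data offer little to check it with. By the assessment schedule at the end of the protocol text, the first pain and satisfaction measurements were taken after the programmes were delivered, and hip function, kinesiophobia and daily-living scores are listed only at the 3rd month. No outcome has a reported value from before the intervention.

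**Working it through.** **1. Is the rule random?** Input: the allocation sentence in Methods. Odd last digit leads to PT, even to VADE. Given the file number, the probability of the assigned arm is 1. No calculation can alter that; the remaining steps ask what the reported data can and cannot show.

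**2. The split.** Inputs: 18 and 13 (Methods). If odd and even digits are equally likely, P(X ≥ 18 | n=31, 0.5) = 0.2366, so the two-sided p = 2 × 0.2366 = 0.473. The split fits the rule having been followed. It says nothing about whether the rule was concealed.

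**3. The five exclusions.** Input: 36 - 31 = 5, or 5/36 = 13.9%. Adding them back in every possible way:

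| Excluded PT:VADE | All 36 by parity | Binomial p |
|---|---|---|
| 0:5 | 18:18 | 1.00 |
| 1:4 | 19:17 | 0.87 |
| 2:3 | 20:16 | 0.62 |
| 3:2 | 21:15 | 0.41 |
| 4:1 | 22:14 | 0.24 |
| 5:0 | 23:13 | 0.13 |

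All six fit chance. The exclusion rates they imply differ widely: 0/18 against 5/18 = 27.8% at one end, 5/23 = 21.7% against 0/13 at the other. These are arithmetic limits, not estimates.

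**4. Baseline age.** Inputs (Table 1): PT 55.33, SD 11.83, n=18; VADE 49.61, SD 9.52, n=13.
- Difference: 55.33 - 49.61 = 5.72 years.
- Pooled SD: √[(17 × 11.83² + 12 × 9.52²)/29] = 10.93.
- Standardised difference: 5.72/10.93 = 0.52.
- SE: 10.93 × √(1/18 + 1/13) = 3.98, so t = 5.72/3.98 = 1.44 on 29 df and p = 0.161. This reproduces the 0.16 in Table 1.
- 95% CI: 5.72 ± 2.045 × 3.98 = -2.42 to 13.86 years, or -0.22 to 1.27 SD.
- By the noncentral t distribution (two-sided 0.05, 29 df), such a test reaches 80% power only at a true gap of 1.055 SD, which is 1.055 × 10.93 = 11.5 years.

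**5. Other continuous baseline variables (Table 1).**
- BMI: 26.86 - 26.07 = 0.79; 0.79/2.61 = 0.30; p = 0.412, against 0.41 reported.
- Daily working time: 5.15 - 2.00 = 3.15; pooled SD √[(17 × 3.67² + 12 × 5.28²)/29] = 4.41; 3.15/4.41 = 0.71; reported p = 0.11 by Mann-Whitney. The plan used a rank test here, so the standardised difference is only a rough guide.

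**6. Reach.** Between-group comparisons printed with p < 0.05:
- Table 2: 3 of 6
- Table 3: 6 of 11
- Table 4: 10 of 10
- Total: 19 of 27

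**The case against.** The best reply is that nothing was hidden. The parity rule stands in the sentence after the label, so a careful reader can see what was done. The study was completed in June 2019 and the allocation cannot be redone, so what remains is a correction of terms. That describes the remedy fairly but does not rescue the label, which still asserts something the next sentence contradicts.

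Second, foreknowledge is inferred from silence. This stands: the documents do not show that anyone used the file number to steer enrolment, and the split gives no sign of it.

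Third, the document has no discussion section, so a limitation may be stated in a fuller report. That cannot be checked here, and it is a reason not to make much of the missing caveat.

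Fourth, the exclusions are partly a separate matter of participant flow. The text may be a retrospective count rather than a sequence, and under a parity rule the timing of an exclusion cannot change anyone's arm. That is right, but refusal or removal can still depend on a foreseeable arm, so the breakdown is needed. The rule also makes it easy to produce, because every file number has a parity.

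Finally, the 27 comparisons are not independent: totals are counted with their subscales, and items recur at two times. The count shows how far one caveat reaches, not how strong it is. Likewise, age should not be read as the main imbalance, since working time differs more.

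**Conclusion.** The concern holds. The allocation is quasi-random by file-number parity, with no concealment described, and should not be called randomised. Confidence is high on the label and on the absence of any described concealment, because both rest on the text alone.

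Whether the results are biased is a different question and is not answered. Selection bias is a risk, not a finding, and the documents give no basis for estimating its size. The baseline tests neither show nor exclude imbalance: at 18 and 13 patients, the age data are compatible with anything from near balance to a gap of more than a decade. The split checks assume that odd and even last digits are equally likely. The extreme exclusion rates assume that all five patients fell on one side.

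**What to change.** 1. In Methods, describe the study as quasi-randomised by file-number parity and drop the reference to systematic sampling. State who screened and invited patients, who could see file numbers before enrolment, and whether anything was concealed.
2. Reconcile the order of exclusion and allocation. As written, exclusions that include missed follow-up come before assignment, although a missed follow-up would normally come after it. Add a short flow table giving the five exclusions by parity, reason and timing. The Methods record that an "informed consent form was signed by all participants"; whether data on people who declined may be used is not stated. If records or consent do not allow the table, say so.
3. Keep the existing tests. With the between-group results and Tables 2 to 4, state that allocation was quasi-random with no concealment described, that selection bias cannot be excluded, and that non-significant baseline tests do not establish balance.
4. Optional: an adjusted analysis of a small number of main outcomes, labelled post hoc and supportive, since no primary outcome is named and the covariates would be chosen after seeing the data. Adjusting for age alone would pass over the larger gap in working time. No adjustment removes unmeasured selection, so this item can be left out.

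The cost is a few sentences and one small table, which depends on records for five patients. The study loses the word randomised; no reported estimate or p-value changes.

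### Week-1 pain and satisfaction scores come from any of the first five postoperative days; the day is neither reported by arm nor accounted for in the comparison

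*Combined protocol and SAP*

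**What the plan says.** The Methods place the first contact in a window, not on a day: "The first meeting with participants was made in the hospital room within the first 5 days after THR surgery in both groups". The first assessment has the same window: "Assessments were performed within the first 5 days after the THR surgery (Descriptive Information, Pain, Patient Satisfaction Questionnaire) in the hospital room". It follows the intervention, being made "in the hospital room after physiotherapy and VADE programs", and no pre-session pain score is described.

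Tables 2 and 4 label these scores as 1st week. Table 1 compares the arms on demographic and surgical characteristics but not on days since surgery.

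For between-group comparison of continuous outcomes, the Statistical Analysis Plan says that "Independent Sample T-Test was used to compare independent group differences" when parametric assumptions hold, with Mann-Whitney U otherwise. It names no covariate or stratification.

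The Results nevertheless report a significant difference on "resting pain levels in the 1st week and on resting and activity pain levels in the 3rd month in favor of the VADE group", and higher week-1 satisfaction with VADE on every item.

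Allocation was by the last digit of the file number (odd to PT, n = 18; even to VADE, n = 13). The same physiotherapist gave both programmes.

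**The concern.** Postoperative pain would be expected to change over the first days after surgery. A patient scored on day 1 and one scored on day 5 are not at the same stage, yet both enter the tables as 1st week. If the mean day of assessment differed between arms, part of a week-1 difference would reflect days since surgery and not the education.

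Nothing in the design prevents such a difference. File-number parity discloses the arm before the visit, the physiotherapist necessarily knew which programme was to be given, and no rule sets the visit day independently of arm.

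Even if day was balanced, pooling days 1 to 5 inflates the within-arm spread and blurs the comparison. The claims at stake are the week-1 rest-pain result and, to a degree that the documents do not allow to be sized, the week-1 satisfaction results.

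**Working it through.** **Inputs.** Table 2, rest pain, 1st week: PT 6.97 ± 1.72 (n = 18), VADE 4.8 ± 2.67 (n = 13). The table gives no unit. Values run up to 10, and I call them points. A two-sided 5% level is assumed, because the plan does not state sidedness.

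**1. Reproduce the reported p-value (0.01).**
- Pooled SD = √[(17 × 1.72² + 12 × 2.67²)/29] = 2.164
- SE = 2.164 × √(1/18 + 1/13) = 0.788
- t = 2.17/0.788 = 2.75 on 29 df, p = 0.010
- 95% CI = 2.17 ± 2.045 × 0.788 = 0.56 to 3.78

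The figure reproduces as an independent-samples test, although the Table 2 footnote labels superscript a as a paired test. As the SDs are unequal, Welch is a fair check: SE 0.844, about 19 df, p = 0.019, lower limit 2.17 − 1.77 = 0.40.

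**2. Shift that removes significance.** This is the lower confidence limit: 0.56 points (pooled) or 0.40 (Welch).

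**3. Convert to days.** The documents give no daily rate of pain decline. I assume a linear fall of 0.3 to 1.0 points per day and read the window as days 1 to 5.
- To lose significance (pooled): 0.56/1.0 to 0.56/0.3, or 0.6 to 1.9 days' difference in mean day.
- To explain the whole difference: 2.17/1.0 to 2.17/0.3, or 2.2 to 7.2 days. The largest possible gap is 4 days, so any rate below 2.17/4 = 0.54 points per day cannot do it.

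**4. Chance imbalance.** If days were uniform over 1 to 5 and unrelated to arm (SD √2 = 1.41), the SE of the gap in mean day is 1.41 × √(1/18 + 1/13) = 0.51. Chance alone would then keep the gap within about ±1.0 day in 95% of cases.

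**5. Error rates.** Simulation with no true effect, 18 and 13 patients, total within-arm SD 2.15, and 20,000 trials per row:

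| Fall per day | Gap in mean day | p < 0.05 | Difference ≥ 2.17 favouring VADE |
|---|---|---|---|
| 0.5 | 0 | 5.2% | 0.3% |
| 0.5 | 1 | 9.3% | 1.7% |
| 0.5 | 2 | 23.7% | 6.8% |
| 1.0 | 0 | 5.0% | 0.3% |
| 1.0 | 1 | 23.1% | 6.6% |
| 1.0 | 2 | 69.4% | 41.5% |

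With day unrelated to arm, the unadjusted test keeps its 5% level. Only a systematic gap inflates it.

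**6. Noise.** Uniform days have variance 2, so day contributes 2b² to a pooled variance of 2.164² = 4.68, where b is the fall per day. That is 0.18/4.68 = 4% at b = 0.3 and 2/4.68 = 43% at b = 1.0.

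**7. Internal evidence on timing.**
- Week-1 sleep pain, same visit: 5.54 − 5.5 = 0.04, 95% CI −1.77 to 1.85. This speaks against a shift as large as 2.17 but does not exclude 0.56.
- Week-1 activity pain: 8.54 − 7.13 = 1.41, in the same direction as rest pain (reported p = 0.13).
- Month-3 rest pain: 3.86 − 2.02 = 1.84, 95% CI 0.47 to 3.21.

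**The case against.** The strongest reply is that the window is identical in both arms, and a shared window adds noise, not bias. That is right, and step 5 confirms it.

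A reader might infer that VADE patients were seen later because their session took about 45 minutes against 30 and needed a presentation. The documents do not support this. Fifteen extra minutes do not imply an extra day, and no text describes scheduling by arm. A chance gap could equally have run the other way and hidden a difference.

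It is also fair to say that any source of bias can be set against a lower confidence limit, that the daily rate is assumed, and that rest pain at week 1 is one of six between-group pain tests in a study whose stated aim does not include pain. Adjusting for day would not supply the missing pre-session score or repair the allocation, so a pre-existing difference between arms remains an open explanation.

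A reader might also infer that the within-group falls in pain are undermined. The documents do not show this. Rest pain fell by 6.97 − 3.86 = 3.11 in PT and 4.8 − 2.02 = 2.78 in VADE, and no between-arm comparison of change is reported.

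What remains is narrow but unanswered: day of assessment is a plausible determinant of week-1 pain, its balance is neither ensured nor shown, and the comparison ignores it.

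**Conclusion.** The point holds as a gap in design and reporting, not as a demonstrated bias. Week-1 scores span five postoperative days, and neither the tables nor the analysis account for the day. A timing shift of 0.56 points (0.40 under Welch) would be enough to make the week-1 rest-pain result non-significant. At an assumed 0.3 to 1.0 points per day, that needs 0.6 to 1.9 days' difference in mean day, and at the steeper rates chance alone could produce it.

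The stronger conclusion that a reader might draw, that the 2.17-point difference is simply an artefact of timing, is not supported. It would need a gap of at least about 2.2 days at the steepest assumed rate. Week-1 sleep pain is equal between arms, and a similar rest-pain gap is still present at month 3, where a few days' difference in week 1 is an unlikely cause.

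The day figures rest on the assumed linear rate and on reading the window as days 1 to 5. The 0.56 rests only on Table 2. No size can be given for satisfaction, because the documents offer no basis for how it changes with day.

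**What to change.** - Derive postoperative day for each patient from the surgery and first-assessment dates, and show its distribution by arm in Table 1.
- Analyse week-1 VAS and satisfaction by ANCOVA with arm and postoperative day in the model. Report adjusted and unadjusted differences with 95% CIs whatever the result. Keeping or dropping the finding should not turn on whether p stays below 0.05.
- If the dates cannot be recovered, state that the week-1 rest-pain difference cannot be separated from timing of assessment, and do not present it as an effect of VADE.

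The cost is one derived variable and one extra model term (one degree of freedom with n = 31), and possibly a less favourable week-1 figure. Data collection ended in June 2019, so this is a matter of reanalysis and reporting and needs no new data if the two dates are on file.
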